- Between 26-30 weeks, all subjects will have a total of 8 ml of blood drawn for the following tests:
 - C-reactive protein (CRP)
 - metabolic panel that includes glucose level
 - the lipid panel (total cholesterol, triglycerides, high-density lipoprotein (HDL) cholesterol, and low-density lipoprotein (LDL) cholesterol)
 - hemoglobin A1c

The blood sample collection form will be completed at each timepoint (Appendix Z)

- For each meal received from ModifyHealth, subjects will be asked to take share a photo (via REDCap using the subject's cell phone number or email, EPIC, or in-person) of the uneaten food.

Data on subjects' history and pregnancy/neonatal outcomes will be collected via EPIC:

- The following data will be collected from EPIC for all subjects
 - Medical history (Appendix HH (Spanish)/Appendix TT(English)))
 - Reproductive, and obstetric history including all prior pregnancy complications/outcomes and neonate outcomes (Appendix II (Spanish)/Appendix UU(English)))
 - Current pregnancy labs (Appendix JJ)
 - Current pregnancy, scans, complications, progress reports, clinic reports, hospital reports
 - Current pregnancy outcomes (Appendix KK)
 - Neonatal outcomes will be collected up to 6-weeks post-delivery including all birth data and complications (Appendix LL)
- Data regarding any adverse events will be collected on the Adverse Event form. (Appendix MM).
- Data collected on data collection forms (Appendix HH-LL) and then transferred to REDCap.

Fig 1. Overview and Intervention

[figure not shown]

Table 3

	Screening/ Enrollment/ Randomization		Between 20-24 weeks of pregnancy		Between 26-30 weeks of pregnancy		Between 34-38 weeks of pregnancy	
	Routine Diet	MedDiet	Routine Diet	MedDiet	Routine Diet	MedDiet	Routine Diet	MedDiet
Informed consent	X	X						
Inclusion/ Exclusion criteria	X	X						
Medical record release	X	X						
Medical, reproductive, & obstetric history*	X	X						

Nutrition (FIGO) checklist	X	X						
Food insecurity screening	X	X						
Diet information & handouts provided	X	X						
Diet and physical activity counseling	X	X	X	X	X	X	X	X
Blood draw for: 1. CRP 2. metabolic panel 3. Lipid panel 4. A1C	X	X			X	X		
MedDiet adherence screening				X		X		X
Routine Diet adherence screening			X		X		X	
6 meals delivered every 3 weeks	X	X	X	X	X	X	X	X
Olive oil and nuts provided		X				X		
Canola oil and healthy snack provided	X				X			
Exercise/food recall and general assessment questionnaire			X	X	X	X	X	X

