Pregnancy data collected*	X	X	X	X	X	X	X	X
Delivery data collected**								
Neonatal data collected**								

*Data will be collected through medical records

**Data will be collected at 6 weeks post-delivery through medical records.

Outcomes

- **Diet Adherence Assessment:** Adherence of both groups will be assessed with a questionnaire based on a validated diet adherence questionnaire³⁹ during counseling sessions as described above. Questionnaires will be scored with a “1” assigned to all responses corresponding to the recommended guidelines and a “0” assigned to all responses which do not correspond to the recommended guidelines. The level of adherence will be defined based on the scale score as: ≤4 low adherence, 5-11 moderate adherence, and ≥ 12 high adherence.
- **GWG:** Total GWG will be calculated by subtracting the participant’s weight (lbs.) at the initial prenatal visit from the weight (lbs.) at time of the delivery or at the last prenatal visit. GWG in the first trimester (6-13 weeks), second trimester (14-26 weeks), and third trimester (27-40 weeks) will also be calculated. Calibrated weight scales will be used at our clinic and at the hospital. Compliance rate of GWG based on IOM guidelines for overweight and obese women¹⁰ will be compared between the MedDiet and the control group.
- **Adverse Pregnancy Outcomes (APO):** We will examine the most common Adverse Pregnancy Outcomes (APO) associated with overweight and obesity (Table 3).^{2,4,5-7,45-51} Definition and management of all APO will follow the standardized guidelines at Myers Park OBGYN clinic.

Table 3 Adverse Pregnancy Outcomes (APO)

APO	Prevalence in Pregnant Women
HDP (preeclampsia, eclampsia, or gestational hypertension)	4-6% of overweight/obese women BMI ≥30 ⁴⁵ 12% in women with a BMI ≥40 ⁴⁶
GDM	6-14% in overweight/obese women ⁴⁷
PTB	10.2% in US in 2021 was 10.2% (www.cdc.gov); data suggest increased risk among overweight/obese women 48-50
Cesarean Delivery	29.9% in NC in 2020 (www.cdc.gov); There is a dose-response relationship between pre-pregnancy BMI and cesarean delivery rate. ^{4,7,51}
Large for Gestational Age (LGA) infant	Data suggestion relationship between LGA (birth weight >90th percentile) and overweight /obese women ^{7,51}

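### A last clinic weight taken at any gestational age can close total weight gain, so a woman who leaves care early is misclassified against full-pregnancy IOM ranges, and no outside records are planned to recover her outcomes

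*Combined protocol and SAP*

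**What the plan says.** **Closing weight.** Under Outcomes, GWG, the first-visit weight is subtracted "from the weight (lbs.) at time of the delivery or at the last prenatal visit". No earliest week is set for that visit. The same paragraph says "Calibrated weight scales will be used at our clinic and at the hospital", and names the comparison between arms: "Compliance rate of GWG based on IOM guidelines for overweight and obese women".

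**Limits.** The Baseline Visit and Trimester Visits sections give the IOM ranges as totals for the whole pregnancy: 15-25 lb for overweight and 11-20 lb for obese women. They are not scaled to weeks observed. The hypothesis under secondary objective 1 is worded differently, in terms of low rates of excessive gain and of adverse pregnancy outcomes (APOs).

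**Source of outcomes.** The methods text says "pregnancy/neonatal outcomes will be collected via EPIC", and the list of items includes "Current pregnancy, scans, complications, progress reports, clinic reports, hospital reports". Table 3 (schedule of activities) has a row "Medical record release", ticked at enrollment in both arms. Its footnote on delivery and neonatal data reads "Data will be collected at 6 weeks post-delivery through medical records".

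**What is not stated.** The protocol text does not say what the release is for, whether outside records will be requested when a woman transfers care, or how an APO is coded when there is no delivery record. The Analytical Plan gives no analysis set, denominator or missing-data rule.

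**The concern.** For a woman who delivers under these clinics' care, the last prenatal visit is normally close to delivery and the rule does little harm. For a woman who moves, changes provider or stops attending, it takes a weight from mid-pregnancy, calls it the total, and compares it with a range meant for a completed pregnancy. The stated rule itself produces the wrong classification; a missing value never arises.

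The protocol describes its population as socially vulnerable and about 51% uninsured, so changes of care are plausible. It also says the findings will be the foundation of larger trials. With 30 women per arm, three women are 10 percentage points, so a few misclassified women can move an estimate that a later trial may be planned on.

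**Working it through.** The plan reports no sample-size calculation, attrition rate or expected GWG, so there is no figure of its own to reproduce. The check is whether the stated rule gives the right class for a woman last weighed early.

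**Inputs from the protocol**
- IOM limits: 15-25 lb (overweight), 11-20 lb (obese).
- First visit at 6-16 weeks; gain counted from that visit.
- 30 women per arm.
- Cesarean background rate 29.9% (table of APOs).

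**Assumptions, not in the protocol**
- Linear gain from the first visit to delivery at week 39.
- First visit at week 12 (range 8 to 16).
- Last weight at week 28 (week 20 also shown).

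**1. Share of final gain seen at week 28**

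Share = (28 - 12)/(39 - 12) = 16/27 = 0.593.

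**2. Upper limit: who escapes the excessive class**

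Largest final gain still recorded at or below the limit = limit / share.
- Overweight: 25/0.593 = 42.2 lb.
- Obese: 20/0.593 = 33.8 lb.

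With a first visit at week 8 the share is 20/31 = 0.645, and these become 38.8 and 31.0 lb. At week 16 the share is 12/23 = 0.522, and they become 47.9 and 38.3 lb.

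**3. Lower limit: who is wrongly called non-compliant**
- Overweight, truly 15-25 lb: recorded at 15 x 0.593 = 8.9 lb to 25 x 0.593 = 14.8 lb. All fall below 15 lb.
- Obese, truly 11-20 lb: 11/0.593 = 18.6 lb, so those heading for 11 to about 18.5 lb are recorded below 11 lb.

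Conversely, overweight women heading for 15/0.593 = 25.3 lb up to 42.2 lb, all truly excessive, are recorded as compliant. The compliance class is wrong in both directions.

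**4. When the excess becomes visible**

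Week of crossing = first week + (39 - first week) x limit / final gain.
- Overweight, heading for 30 lb: 12 + 27 x 25/30 = week 34.5. At week 28 she shows 17.8 lb (within range), at week 20 8.9 lb (below).
- Obese, heading for 25 lb: 12 + 27 x 20/25 = week 33.6. At week 28 she shows 14.8 lb (within range), at week 20 7.4 lb (below).

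For first visits at weeks 8-16 and final gains of 30-35 lb (overweight) or 25-30 lb (obese), crossing falls between weeks 28.7 and 35.2.

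**5. Effect on the excessive-gain rate**

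Fall in the observed rate = true rate x share of excessive leavers reclassified x proportion leaving. For illustration, assume a true rate of 50% and 80% reclassified:

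| Leaving | Fall in rate |
|---|---|
| 5% | 0.5 x 0.8 x 0.05 = 2 points |
| 10% | 0.5 x 0.8 x 0.10 = 4 points |
| 20% | 0.5 x 0.8 x 0.20 = 8 points |
| 30% | 0.5 x 0.8 x 0.30 = 12 points |

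If the diets do not differ, equal leaving with the same timing gives no false difference. Leaving of 10% against 30% (3 against 9 of 30) gives 12 - 4 = 8 points, or 10 points if all are reclassified.

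**6. APOs, only if a leaver were coded as having no event**

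False difference = rate x difference in leaving. For cesarean with 10% against 30% leaving: 29.9% x 0.20 = 6.0 points. With 30 per arm and two-sided alpha 0.05 (assumed), the chance of a significant result is then about 8%. The plan does not state this coding, so the figure is conditional.

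**The case against.** A reader might infer that outcomes come only from EPIC and that leaving care is scored as no adverse outcome. The documents do not support that:
- No section says that an event absent from the chart is coded as no.
- Preterm birth, cesarean and large-for-gestational-age need a delivery date, mode or birth weight. Without a delivery those fields may simply be blank and the woman dropped from the denominator, which is a selection problem of a different kind. The outcome forms that would settle this (Appendices KK and LL) are not reproduced.
- The EPIC extraction includes hospital reports, so some deliveries after leaving the clinics would still be seen. GDM or hypertension diagnosed before she left stays in the chart.
- The footnote speaks of medical records in general, and a release is obtained. Outside records are allowed; they are just not planned.

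A reader might also infer that attrition always looks like benefit. That holds only for the excessive-gain rate in the hypothesis. For IOM compliance, the comparison the Outcomes section names, step 3 shows errors both ways, and the net direction depends on exit week and the distribution of gain.

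Three further objections have force. The attrition and reclassification figures are assumptions. Consent pages are not available, so terms separating stopping the diet from withdrawing record follow-up may exist there. And this is a 60-woman pilot whose primary objective is feasibility and adherence, with efficacy explicitly preliminary.

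None of this answers the closing-weight rule, which is written down and has no gestational-age limit. That a very early exit can score below range is a further reason not to classify from such a weight.

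**Conclusion.** The concern holds for GWG. A last-visit weight well before delivery misclassifies a woman against full-pregnancy limits. With linear gain from week 12 to 39, a week-28 weight hides excessive totals up to about 42 lb (overweight) or 34 lb (obese), and turns every overweight woman on course for 15-25 lb into a non-complier. The bias in the excessive-gain rate is downward. For the compliance rate its direction cannot be stated in advance. Bias between arms needs unequal or outcome-related leaving, and the documents give no rate for either.

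For APOs the finding is narrower: no request for outside records is planned and no coding is stated when there is no delivery record.

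The harm is distorted pilot estimates on secondary objective 1 rather than false significance. The primary objective is not affected. The change is worth making because it is cheap and the release is already obtained.

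**What to change.** 1. State that the release obtained at enrollment will be used to request the delivery weight, delivery record and neonatal record for women who deliver elsewhere, whether or not they continued the diet, unless consent for record follow-up is withdrawn.
2. Accept a last-visit weight as the closing weight only within a pre-stated window before delivery. Otherwise treat total GWG and IOM compliance as missing. Gain per week against gestational-age-adjusted limits can be a secondary analysis.
3. Code delivery-dependent APOs as missing when there is no delivery record. Keep outcomes diagnosed before the woman left.
4. Report the number of women with known GWG and known APO status by arm.

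The cost is protocol wording, a few records requests with the abstraction time they need, and some outcomes reported as missing. Participants carry no added burden.

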Therefore, if our study is successful in implementing a sustainable evidence-based dietary program, the next step will be to establish a specialized nutritional prenatal care service designed to prevent clinical complications and improve pregnancy outcomes. This will involve

increasing the dedicated time and frequency of comprehensive dietary counseling sessions during gestation. These sessions will be independent from routine prenatal care visits. In addition, we plan to work with local government and private healthy diet organizations to help socially vulnerable pregnant women overcome nutritional challenges.

Objectives and Hypothesis

Primary Objective

To examine the feasibility and adherence to a MedDiet program initiated in the first or early second trimester of gestation (6-16 weeks) among overweight and obese women.

Hypothesis: Overweight and obese pregnant women enrolled in the MedDiet program have an elevated level of adherence facilitated by the design of a comprehensive dietary program with free home-delivered meals, nuts, and EVOO bottles. This hypothesis will be tested by examining adherence to the MedDiet program using a validated screening tool.³⁹

Secondary Objectives

1. To estimate the preliminary efficacy of a MedDiet intervention controlling gestational weight gain and reducing adverse pregnancy outcomes (APO).

Hypothesis: Overweight or obese pregnant women consuming MedDiet have low rates of excessive gestational weight gain and adverse pregnancy outcomes. This hypothesis will be tested by comparing gestational weight gain and pre-selected pregnancy outcomes between women allocated in each dietary group.

2. To estimate the preliminary impact of MedDiet intervention on maternal cardiometabolic profile.

Hypothesis: MedDiet leads to favorable effects on cardiovascular clinical parameters and cardiometabolic biomarkers in pregnancy. This hypothesis will be tested by comparing maternal cardiovascular parameters trends and cardiometabolic biomarkers during pregnancy among the studied groups.

Methods and Measures

Study Design

Type of study

This is a prospective, randomized, pilot study with a behavioral intervention. Sixty participants diagnosed as overweight ($BMI 25.0-29.9 \text{ kg/m}^2$) or obese ($BMI \geq 30.0 \text{ kg/m}^2$) in the first or early second trimester of gestation will be invited to participate.

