Participants will be randomized to a MedDiet program or the currently offered American College of Obstetricians and Gynecologists (ACOG)-based dietary counseling program at Myers Park and North Park OBGYN Clinic(s) in Charlotte, North Carolina.

Duration of Study and Participating Site

This will be a multi-center study including Myers Park OB/GYN Clinic and North Park OB/GYN Clinic which are academic obstetrical practices providing prenatal care to a socially vulnerable and highly racial/ethnic diverse population. All new scheduled prenatal visits will be screened in Epic for eligibility by our research team.

We anticipate full completion of the study by July 2025.

Study population (Table 1)

Inclusion Criteria	Exclusion Criteria

• Viable singleton pregnancy in the first trimester (6 0/7- 16 6/7 weeks); includes twins reduced to singleton spontaneously or vanishing twin syndrome• BMI $\geq 25.0 \text{ kg/m}^2$; calculated by dividing maternal weight in kilograms by height in meters squared using a calibrated scale and standard metric measure (BMI calculator available at www.cdc.gov)• Confirmed intrauterine pregnancy by ultrasound exam (6-16 weeks)• Age 18 years or older• Primary language of English or Spanish	
• BMI $< 25.0 \text{ kg/m}^2$• Known pre-pregnancy diabetes• Hemoglobin glycosylated (A1C) $> 5.7\%$ at first prenatal visit• Pre-pregnancy hypertensive disease• Non-viable pregnancy• Known allergies to an essential component(s) of MedDiet• Inability to read or write in primary language• Mental incapacity to make medical decisions• Food insecurity

Sample Size

Since this is a pilot study, we aim to enroll 60 participants with 30 per study arm. Based on the patient population at Myers Park, we anticipate the following racial/ethnic breakdown of subjects.

Table 2 Anticipated Enrollment (all subjects will be female)

Race	Non-Hispanic	Hispanic	Total
Asian	1	0	1
Black or African American	15	0	15
White	6	36	42
More than One Race	2	0	2
Total	24	36	60

Methods and Intervention

- Fig 1 and Table 3 provide a detailed view of the study activities.
- With the purpose of overcoming language barriers, the dietary program was developed in English and Spanish. Multiple aids were created including practical educational tools, recipes, shopping list, and meal portion guidance to improve engagement and enhance sustainability.

Randomization and Study Groups:

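### Total GWG starts at a first visit anywhere in 6 0/7-16 6/7 weeks but is judged against whole-pregnancy IOM limits, and first-trimester GWG has no stated start weight for late entrants (minor)

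*Combined protocol and SAP*

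**What the plan says.** - **Total GWG** (Outcomes, GWG): found by subtracting "weight (lbs.) at the initial prenatal visit from the weight (lbs.) at time of the delivery or at the last prenatal visit". Neither weight is tied to a gestational age, and no order of preference is given between the two end weights. "Calibrated weight scales will be used at our clinic and at the hospital", so the end weight may come from either place.
- **Compliance** (same paragraph): "Compliance rate of GWG based on IOM guidelines for overweight and obese women" is compared between arms. The only IOM limits in the document are the total ranges used for counselling (Baseline Visit and Trimester Visits): 15-25 lb for overweight and 11-20 lb for obese women.
- **Trimester gains** (same paragraph): "GWG in the first trimester (6-13 weeks), second trimester (14-26 weeks), and third trimester (27-40 weeks) will also be calculated".
- **Entry window**: Table 1 requires "Viable singleton pregnancy in the first trimester (6 0/7- 16 6/7 weeks"; the Primary Objective describes a programme "initiated in the first or early second trimester of gestation (6-16 weeks".
- **Hypothesis and test** (Secondary Objectives): women on MedDiet "have low rates of excessive gestational weight gain and adverse pregnancy outcomes", tested by "comparing gestational weight gain and pre-selected pregnancy outcomes between women allocated in each dietary group".
- **Analysis** (Analytical Plan): t-tests or ANOVA for continuous variables, chi-square for proportions, and a regression with no covariates named. Adjustment for gestational age is possible but not specified.

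**The concern.** A whole-pregnancy limit is applied to a part-pregnancy gain. To 40 weeks, a woman entering at 6 0/7 is observed for 34.0 weeks and one entering at 16 6/7 for 23.1 weeks, yet both face the same limits. Women near a limit can be classed differently because of when they first attended. At stake is the meaning of the absolute rates. They will be reported descriptively, and the Background presents the pilot as the basis for larger trials.

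The trimester outcome has a separate gap. It ends the first trimester at 13 weeks, but enrolment runs to 16 6/7. If the initial-visit baseline also applies here, a woman entering from 14 0/7 has no start weight for this outcome. The document also uses the term first trimester inconsistently: Table 1 applies it to the whole entry window, the Primary Objective calls the window first or early second trimester, and Outcomes stops at 13 weeks.

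**Working it through.** The plan states no figure to reproduce; it says that no sample size was calculated.

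**Inputs from the document:** entry 6 0/7-16 6/7 weeks; upper limits U = 20 lb (obese) and 25 lb (overweight); lower limits 11 and 15 lb; 30 women per arm.

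**Assumptions, not in the document:** gain to 40 weeks, T, is normal with mean 22 lb (obese) or 27 lb (overweight) and SD 12 or 14 lb; early gain e by week 13 is fixed between -2 and 4.4 lb; gain is linear before and after week 13; entry is uniform over weeks 6-17.

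**1. Spans.** 40 - 6 = 34.0 weeks; 40 - 16.857 = 23.1 weeks.

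**2. One woman exactly at the upper limit, entering at 16 6/7.** Uncounted gain = e + (U - e)/27 × 3.857.
- U = 20: 2.9 lb (e = 0) to 6.6 lb (e = 4.4).
- U = 25: 3.6 lb to 7.3 lb.

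**3. Group rates.** For entry at week t, counted gain is T - e·t/13 if t ≤ 13, and (T - e)(40 - t)/27 if t > 13. Gain is classed as excessive when T exceeds U + e·t/13, or e + 27U/(40 - t), respectively. Example (obese, SD 12, e = 4.4, all entering at 11.5 weeks): the threshold is 20 + 4.4 × 11.5/13 = 23.89. The rate is 1 - Φ(1.89/12) = 0.437, against 1 - Φ(-2/12) = 0.566 for the whole pregnancy, a change of -12.9 points. Averaging over entry week, across both BMI groups and both SDs (change in percentage points):

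| Early gain e | Excess rate, uniform entry | Excess rate, all enter at 11.5 wk | Within-range rate, uniform entry |
|---|---|---|---|
| -2 lb | +2.5 to +3.4 | +4.9 to +5.7 | -0.7 to -0.3 |
| 0 lb | -2.5 to -1.7 | 0 | +1.0 to +1.5 |
| 4.4 lb | -14.4 to -12.0 | -12.9 to -11.1 | +2.7 to +4.6 |

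At 4.4 lb, removing all spread in entry leaves about 11-13 points, so variable entry adds only about 1-1.5. At zero early gain the whole effect, about 2 points, comes from women entering after week 13.

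**4. Sampling error of one arm's rate.** 1.96 × √(0.56 × 0.44/30) = 17.8 points.

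**5. Arm comparison, entry timing.** SD of entry week = 11/√12 = 3.18. SE of the arm difference = 3.18 × √(2/30) = 0.82 weeks. At 0.1-0.5 lb uncounted per week this is 0.08-0.41 lb of chance imbalance, against a sampling SE of 12 × √(2/30) = 3.1 lb. In simulated trials (SD 12, 30 per arm) the SE was 2.88-2.90 lb unadjusted and 2.89-2.91 lb adjusted for entry week.

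**6. Arm comparison, end timing.** At an assumed 0.5-1 lb per week, each week of difference between arms in the timing of the last weight moves mean GWG by 0.5-1 lb.

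**7. First-trimester GWG.** 14 0/7-16 6/7 is 21 of 77 entry days: 21/77 = 27%, about 16 of 60 women under uniform entry.

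**The case against.** **The planned use is between arms, and randomisation protects it.** This largely stands. Compliance is to be compared between groups, and even the low-rates hypothesis is to be tested by comparison. A reader might infer that variable entry biases the trial's GWG result. The document does not support that: entry week is fixed before allocation and cannot differ systematically by arm. The within-range difference can be somewhat attenuated when early gain goes uncounted. With assumed arm means of 27 and 22 lb and SD 10-15 lb, the loss was about 0-3 points counting from week 6 and up to 7 in an extreme case, against a sampling SE of about 12 points. The protection does not extend to the end weight, which is measured after randomisation and may shift if diet affects delivery timing.

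**The large figure is not about entry spread.** This stands. It is tempting to attribute all 12-14 points to the 11-week window; most of it would remain if every woman entered at 11.5 weeks.

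**Every size is assumed, and the sign can reverse.** This stands for the size. The omission itself can be read directly from the text.

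**An earlier weight may exist.** This stands in part. The initial-visit baseline is stated only for total GWG. Screening and Recruitment mentions pregnancy confirmation visits and collects BMI, clinic reports are drawn from EPIC, and the Appendix lists a first-trimester form that is not reproduced. A reader might infer that first-trimester GWG is impossible for late entrants; the document shows only that no start weight is named for them.

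**Scaling the limits may be worse than leaving them.** This stands as a caution. An assumed early gain wrong by 2.2 lb moves the excess rate by about 5-6 points, more than the unscaled error at zero early gain.

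**Conclusion.** The point holds, at minor severity: it concerns a secondary outcome of an unpowered pilot. As written, the IOM rates describe gain since the first visit judged against whole-pregnancy limits, so women near a limit can be misclassified. Under the stated assumptions the excess rate is understated by about 2 points at zero early gain and 12-14 points at 4.4 lb, with the sign reversing under early loss. The within-range rate, the more natural reading of compliance, moves by about 1-5 points over the same range of early gain. Both are smaller than one arm's sampling error, although enrolling more women would not remove them.

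The arm comparison is barely affected by entry timing; no such assurance is available for end timing. The first-trimester gap follows from the stated windows if the initial-visit baseline applies. The 27% rests on uniform entry.

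**What to change.** These changes concern analysis and reporting only; the counselling ranges and the entry window are not at issue.

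1. **Arm comparison.** Replace the unadjusted t-test with an ANCOVA of last weight, adjusted for enrolment weight, gestational age at enrolment and the BMI category used in randomisation. Do not adjust for gestational age at delivery, which diet may affect.
2. **IOM compliance.** Apply one end-weight rule to all women. Report gestational age at first and last weight by arm. State whether compliance means within range or not above it, and label the rate as gain since the first visit. Limits scaled to weeks observed are optional, as a sensitivity analysis under more than one assumed early gain.
3. **First-trimester GWG.** Report it descriptively, only for women with a weight before 14 weeks, with the number contributing. Reconcile the first-trimester wording across the Primary Objective, Table 1 and Outcomes.

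**Cost:** some SAP wording and a little more analysis. Gestational age is already collected at screening and clinic records are already drawn from EPIC. Adjusting for entry week brings little or no precision; it guards against chance imbalance in entry timing, about 1.6 weeks either way (1.96 × 0.82). The gain is a rate that readers can interpret.

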- **Cardiovascular parameters:** MedDiet is associated with reduction of blood pressure (BP) in non-pregnant adult overweight or obese women.⁵² Physiological changes of blood pressure (BP) during pregnancy are characterized by reduction of BP in the second trimester with return to the pre-pregnancy level late in the third trimester and postpartum period.⁵³ Heart rate (HR) increases by 20% to 25% over baseline during gestation.⁵⁴ Maternal BP and HR will be obtained by a calibrated automated oscillometric device during prenatal visits from the first to the third trimesters following the standardized technique established in our clinic. Trends of BP and HR throughout gestation will be compared among women allocated in the intervention and the control groups.
- **Cardiometabolic biomarkers:** Consumption of MedDiet is associated with lower levels of total cholesterol,⁵³ reduces insulin resistance preventing type 2 diabetes^{30,31} and GDM,^{34,36} and reduces markers of subclinical inflammation such as C-reactive protein (CRP).⁵⁵ Pregnancy is characterized by increased levels of total cholesterol, low-density lipoprotein (LDL), high-density lipoprotein (HDL), and triglycerides, especially in the second and third trimester,⁵⁶ and pregnancy is a state of increased insulin resistance.⁵⁷ There is limited knowledge about the effect of MedDiet on cardiometabolic biomarkers during pregnancy. Maternal lipid profile, random glucose level, hemoglobin A1C, and CRP levels will be compared at baseline (6-16

weeks) and at 26-30 weeks of gestation among participants in the intervention and the control groups. The labs will be obtained at the same time of scheduled blood draws for routine prenatal labs.

Analytical Plan

This is prospective randomized pilot study of sixty participants who will be randomly allocated in the MedDiet group or in the control group. Because this is a pilot study, a sample size was not calculated. Results will be analyzed initially using descriptive statistics. Comparison between groups will be done using chi square tests for proportions, and t-tests or ANOVA procedures for continuous variables. Regression analysis will be performed to identify independent outcome predictors. Other inferential statistical analysis will be conducted as appropriate.

Human Subjects Protection

Screening and Recruitment

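### Stratifying the cesarean comparison by previous cesarean, which is already collected, would tighten it at no cost; the planned chi-square is unbiased but less precise than it could be

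*Combined protocol and SAP*

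**What the plan says.** **Eligibility.** Table 1 under Study population admits any "Viable singleton pregnancy in the first trimester (6 0/7- 16 6/7 weeks") that meets the other criteria. Neither column mentions parity or previous cesarean.

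**Randomization.** Randomization and Study Groups names BMI category (overweight or obese) as the only balancing factor. The Sample Size section states: "we aim to enroll 60 participants with 30 per study arm".

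**Outcome.** In the adverse pregnancy outcomes (APO) table under Outcomes, the row is simply cesarean delivery, with the background "29.9% in NC in 2020 (www.cdc.gov); There is a dose-response relationship between pre-pregnancy BMI and cesarean delivery rate". On definitions, the text above the table says: "Definition and management of all APO will follow the standardized guidelines at Myers Park OBGYN clinic". Those guidelines are not reproduced.

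**Analysis.** The Analytical Plan says: "Comparison between groups will be done using chi square tests for proportions". It adds a regression to find independent outcome predictors and further inferential analysis as appropriate, but names neither outcomes nor covariates. It also says: "Because this is a pilot study, a sample size was not calculated".

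**Data available.** The list of items taken from the electronic record includes "Reproductive, and obstetric history including all prior pregnancy complications/outcomes and neonate outcomes".

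**The concern.** Previous cesarean is fixed before randomization and can be expected to predict mode of delivery strongly. The protocol collects the information but gives it no stated role in allocation or analysis. An unadjusted comparison leaves the variation between women with and without a previous cesarean in the error term. It also reports one pooled rate in which repeat and first cesareans cannot be told apart.

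The stake is modest but real. Among the APOs for which the table gives a rate, cesarean has the highest (29.9%, against 10.2% for preterm birth, 6-14% for gestational diabetes and 4-12% for hypertensive disorders; large for gestational age has no rate). The background section intends the findings as the foundation for larger trials, and a pooled rate with an unnecessarily wide interval is a weaker basis for planning one.

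**Working it through.** The plan has no sample size, power or event figure for cesarean to reproduce.

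**Inputs from the documents.** 30 women per arm; overall cesarean rate p = 0.299.

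**Assumptions not in the documents.** Share of women with a previous cesarean, q = 10-25%; probability that such a woman delivers by cesarean again, r = 75-90%. The overall rate is held at 29.9%, so the rate in women with no previous cesarean is p0 = (p - q·r)/(1 - q).

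**1. Precision of the planned comparison.** Expected cesareans: 60 × 0.299 = 17.9. SE of the raw difference = √(2 × 0.299 × 0.701/30) = 0.118. 95% half-width = 1.96 × 0.118 = 0.232, about 23 points.

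**2. Share of repeats, q·r/p, and first cesareans, 60(p - q·r).** The extremes are:
- q = 10%, r = 75%: 0.075/0.299 = 25% repeats; 17.94 - 4.5 = 13.4 first cesareans.
- q = 25%, r = 90%: 0.225/0.299 = 75% repeats; 17.94 - 13.5 = 4.4 first cesareans.

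**3. Effect of a chance imbalance of three women, 3(r - p0)/30.**
- q = 10%, r = 75%: p0 = 0.249, shift = 3 × 0.501/30 = 5.0 points.
- q = 25%, r = 90%: p0 = 0.099, shift = 3 × 0.801/30 = 8.0 points.

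Against the 23-point half-width this is roughly a fifth to a third.

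**4. How often such an imbalance occurs.** This is a hypergeometric split of K women with a previous cesarean among 60 into 30 and 30. With equal arms the difference has the same parity as K, so for even K a difference of at least 3 means at least 4.

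| K (share of 60) | P(difference ≥ 3) |
|---|---|
| 6 (10%) | 0.195 |
| 9 (15%) | 0.472 |
| 12 (20%) | 0.333 |
| 15 (25%) | 0.552 |

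**5. Gain from stratifying.** The share of outcome variance explained by previous cesarean is q(1 - q)(r - p0)²/[p(1 - p)], with p(1 - p) = 0.2096. The interval narrows by 1 - √(1 - share).

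| q | r | p0 | Variance share | Interval narrower by |
|---|---|---|---|---|
| 10% | 75% | 0.249 | 0.108 | 5.5% |
| 10% | 90% | 0.232 | 0.192 | 10.1% |
| 15% | 75% | 0.219 | 0.171 | 9.0% |
| 15% | 90% | 0.193 | 0.304 | 16.6% |

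These are large-sample values. Averaging the Mantel-Haenszel variance Σw·v/(Σw)² over the same hypergeometric splits (per stratum, w = n1·n0/(n1 + n0) and v = rate × (1 - rate)) gives gains about one percentage point smaller: 4.7-8.9% at q = 10% and 8.2-15.6% at q = 15%.

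**6. Restricting to first cesareans instead.** At q = 15% there are 30 × 0.85 = 25.5 women per arm. SE = √(2·p0(1 - p0)/25.5) = 0.116 (r = 75%) or 0.110 (r = 90%), which is 2-6.5% below 0.118. Most of the precision gain therefore comes from stratifying, not from restricting.

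**The case against.** The strongest reply is that nothing here is an error. All cesareans compared between randomized arms is a legitimate outcome and estimates the effect on total cesareans without bias. Chance imbalance in previous cesarean is already part of the sampling variation that the chi-square test and its interval allow for. That stands. A reader might infer that the comparison is biased or its type I error inflated; the design described in the documents does not support this.

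Three other stronger readings also fail:
- *Repeat cesareans will dominate the result.* The documents give neither the previous-cesarean share nor the repeat rate. At 10% prevalence repeats are only 25-30% of events, and a three-woman imbalance is small beside the existing noise. Holding the total at the statewide 29.9% may also overstate the repeat share, because the same table row says that the cesarean rate rises with BMI.
- *Cesarean carries most of the information for the first secondary objective.* That objective names gestational weight gain first, and the rates given for the other APOs add up to 20.2% (4 + 6 + 10.2) to 36.2% (12 + 14 + 10.2), before large for gestational age.
- *The outcome should be replaced by first cesarean.* That is debatable. It gains little precision at 15% prevalence and leaves about 4-13 events in the whole trial. The argument that diet hardly affects a repeat cesarean is clinical reasoning, not a statement in the documents.

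The plan's regression could include previous cesarean, so it would be too strong to say that the history goes unused. But no covariate is named. The objections leave the case for a named, stratified analysis untouched.

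**Conclusion.** The point holds as an improvement in precision and clarity, not as a correction of an invalid analysis. At an assumed previous-cesarean share of 10-15%, and a repeat rate of 75-90%, stratifying narrows the interval by about 5-17%, slightly less in a sample this small. A half-width of about 23 points would become roughly 19-22 points (0.232 × 0.834 to 0.232 × 0.945). Repeats could be anywhere from a quarter to three quarters of the events over the full assumed range, so a pooled rate alone is hard to interpret.

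Confidence in the textual facts is high, subject to the clinic guidelines not being visible. The sizes depend on the two assumed inputs. This concerns one APO within one secondary objective of a feasibility pilot, which remains underpowered for cesarean either way.

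**What to change.** In the Analytical Plan:
- Keep all cesareans as the outcome. Report the difference between arms as a Mantel-Haenszel risk difference with 95% confidence interval, stratified by previous cesarean (yes/no) from the reproductive and obstetric history form.
- Report descriptively, by arm, the number of women with a previous cesarean and the first-cesarean rate among women without one. This supplements the all-cesarean result and does not replace it.

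Previous cesarean is a pre-randomization fact, so stratifying on it preserves the randomized comparison. The cost is a few sentences of analysis wording: no new data, visits or change to randomization. The previous-cesarean stratum may hold only 6-15 women (10-25% of 60), so its own rate should not be over-read.
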